CSR	clinical study report
DSST	digit symbol substitution test
EEG	electroencephalogram
ECG	electrocardiogram
HB	hypoxic burden
ICF	informed consent form
KSS	Karolinska sleepiness scale
LS	least square
MedDRA	medical dictionary for regulatory activities
mITT	modified intent to treat
NAW	number of awakenings
NREM	non-rapid eye movement
ODI	oxygen desaturation index
OSA	obstructive sleep apnea
PP	per protocol
PSG	polysomnography
PT	preferred term
REM	rapid eye movement
SAE	serious adverse event
SaO ₂	oxygen saturation
SAP	statistical analysis plan
SE	sleep efficiency

Abbreviation	Definition
SOC	system organ class
SOL	sleep onset latency
TEAE	treatment-emergent adverse event
TST	total sleep time
WASO	wake after sleep onset
WHO	world health organization

1. INTRODUCTION

This statistical analysis plan (SAP) is based on the Protocol # APC-004 Version 2.0, dated 06 January 2021, titled “Phase 2 Randomized Double-Blind Placebo-Controlled 3-Period Single-Dose Crossover Study to Evaluate the Safety and Efficacy of Two Doses of AD-109 in Mild to Moderate Obstructive Sleep Apnea.” Apnimed is developing the combination of atomoxetine and oxybutynin for the treatment of obstructive sleep apnea (OSA). Initial Phase 2 studies of the combination were conducted with marketed oxybutynin (combination designated AD-036), which is a racemic mixture of R- and S-oxybutynin. Subsequent development is being pursued with R-oxybutynin (combination designated AD-109), a new enantiomerically pure form of oxybutynin which is proposed to have an improved safety and efficacy profile in OSA compared to racemic oxybutynin.

Previous studies of AD-036 provided dose-response efficacy and safety data across a broad spectrum of OSA disease severity. Study APC-004 is designed to extend and confirm these findings to AD-109 in a population with mild-to-moderate OSA, in parallel with other studies of AD-109 planned by Apnimed in moderate-to-severe OSA. Study APC-004 is a randomized, double blind, placebo-controlled, 3-period, single-dose crossover study in patients with mild-to-moderate OSA.

This document details the statistical methods planned to perform the final analyses of this study. The reader interested in detail on study rational, study design, and medical background is invited to refer to the study protocol.

2. OBJECTIVES AND ENDPOINTS

2.1. Objectives

2.1.1. Primary Objective

The primary study objective is to compare the efficacy and safety of a higher dose (atomoxetine 75 mg + R-oxybutynin 2.5 mg; 75/2.5) and lower dose (atomoxetine 37.5 mg + R-oxybutynin 2.5 mg; 37.5/2.5) of AD109 to each other and to placebo in the treatment of mild-to-moderate OSA.

2.2. Endpoints

2.2.1. Primary Endpoint

The primary efficacy endpoint is change in \log_{10} of Hypoxic Burden (HB) 4% plus one (scored in reference to AHI[4%]), 75/2.5 dose vs. placebo

2.2.2. Secondary Endpoints

The secondary efficacy endpoints are as follows:

- Change in $\log_{10}(\text{HB}[4\%] + 1)$, 37.5/2.5 dose vs. placebo and vs. 75/2.5
- Change in Apnea Hypopnea Index (AHI) 4%
- Change in Oxygen Desaturation Index (ODI) 4%

- Total time with $\text{SaO}_2 < 90\%$, PSG nights
- Proportion of participants with $\geq 50\%$ reduction in AHI(4%), HB(4%), and ODI(4%)

2.2.3. Tertiary Endpoints

The tertiary efficacy endpoints are as follows:

- Karolinska Sleepiness Scale (KSS) score
- Sleep Quality VAS
- OSA endotype endpoints (Vpassive, Vactive, Muscle Compensation, Loop Gain)
- PSG sleep and arousal parameters
 - Sleep stages distribution and percentage of total sleep time (TST) in the various sleep stages
 - Sleep Efficiency (SE)
 - Wake After Sleep Onset (WASO)
 - Number of Awakenings (NAW)
 - Sleep Onset Latency (SOL)
 - Percentage of total sleep time (TST) spent in sleep stage N1 (Stage N1%)
 - Percentage of TST spent in sleep stage N2 (Stage N2%)
 - Percentage of TST spent in sleep stage N3 (Stage N3%)
 - Percentage of TST spent in sleep stage R (Stage R%)
 - Snoring index
 - Arousal indices (respiratory and spontaneous)
 - Fraction of hypopneas
- Alternate measures of AHI, ODI and HB
 - AHI(4%) in non-rapid eye movement (NREM) sleep
 - AHI(4%) in rapid eye movement (REM) sleep
 - AHI(4%) adjusted for position
 - AHI(3% or arousal)
 - HB(3% or arousals)
 - HB(Total)
 - ODI(3%)

2.2.4. Safety Endpoints

The safety endpoints are as follows:

- Vital signs, clinical laboratory assessment, electrocardiogram (ECG)

- Spontaneous adverse events, including the post-dosing period
- Digit Symbol Substitution Test (DSST)
- PSG parameters:
 - Heart rate (HR)
 - Total time with $\text{SaO}_2 < 90\%$

3. INVESTIGATIONAL PLAN

3.1. Study Design

[figure not shown]
Study APC-004 is a randomized, double blind, placebo-controlled, 3-period, single-dose crossover study in patients with mild-to-moderate OSA. A screening visit and polysomnographic (PSG) exam will be conducted to establish that each participant meets study enrollment criteria. Each participant will then receive a single dose of each of the following during 3 overnight PSG exams, each separated by a one week washout period:

- A: Atomoxetine 75 mg + R-oxybutynin 2.5 mg (i.e., 75/2.5)
- B: Atomoxetine 37.5 mg + R-oxybutynin 2.5 mg (i.e., 37.5/2.5)
- C: Placebo

Efficacy and safety endpoints will compare the 75/2.5 and 37.5/2.5 doses to each other and to placebo.

Each PSG night is followed by a 1-week washout period. Adverse event (AE) and serious adverse event (SAE) information is recorded at each study visit and by telephone contact with participants during each washout period. The overall study duration will be up to 12 weeks (see Figure 1).

Figure 1: Overview of Study Design

PSG = polysomnography.

3.2. Treatment

Study treatment is defined as any investigational treatment(s), marketed product(s), placebo, or medical device(s) intended to be administered to a study participant according to the study protocol.

One tablet of co-formulated atomoxetine and R-oxybutynin or matching placebo is taken immediately before the participant's planned bedtime.

Study Treatment Name:	Atomoxetine hydrochloride/R-oxybutynin chloride	Atomoxetine hydrochloride/R-Oxybutynin chloride	Placebo
Dosage Formulation:	Tablet	Tablet	Tablet
Dosage Level:	37.5mg / 2.5mg	75mg / 2.5mg	N/A
Route of Administration:	Oral	Oral	Oral
Dosing Instructions:	1 tablet administered with up to 240 mL water	1 tablet administered with up to 240 mL water	1 tablet administered with up to 240 mL water
Storage/Packaging/Labeling:	Store at room temperature, in HDPE bottles	Store at room temperature in HDPE bottles	Store at room temperature in HDPE bottles

3.2.1. Randomization Scheme and Treatment Arm Assignment

The planned randomization scheme will utilize randomly ordered blocks with 5 blocks of size 6, with each block randomizing one participant to each of the following 6 sequences: ABC, ACB, BAC, BCA, CAB, CBA. For example, a participant randomized to "ABC" will receive the

treatment sequence: 1.) Atomoxetine 75 mg + R-oxybutynin 2.5 mg; 2.) Atomoxetine 37.5 mg + R-oxybutynin 2.5 mg; 3.) Placebo.

Participants who withdraw from the study will not be replaced.

3.2.2. Blinding

The investigator, study personnel and participant will be blinded to the identity of the study drug in all treatment periods. The CRO staff dealing with blinded site study staff will also be blinded. The Sponsor, Medical Monitor, CRO's Drug Safety and Pharmacovigilance staff, as well as site personnel required for drug administration will also be blinded. The centralized PSG technologists will be blinded to treatment assignment.

The CTI unblinded statistician who reviews the production randomization list will be unblinded to the treatment sequence a participant receives; however, this individual will not have access to study data prior to study completion. The investigational pharmacist and/or the study coordinator, depending on the site, will be unblinded to treatment assignment for the purposes of preparing, controlling, dispensing study product and documenting accountability of study product.

3.2.3. Dosing Schedule

There are 3 randomized crossover PSG nights. The participant will receive one treatment on each of the 3 PSG nights, separated by at least a one-week washout period. Dosing of the study treatment will occur immediately prior to lights out.

3.2.4. Study Treatment Compliance

Only participants enrolled in the study treatments and only authorized site staff may supply or administer study treatments.

After receiving Sponsor approval in writing, sites are responsible for returning all unused or partially used study treatment to the Sponsor or designated third party or for preparing the study treatment for destruction via incineration.

4. GENERAL CONSIDERATIONS FOR DATA ANALYSIS

In general, continuous variables will be summarized by presenting the set sample size (N), number of participants with available data (n), mean, standard deviation (SD), median, minimum, and maximum. In summaries of change from baseline safety variables, only participants with both baseline and post baseline data will be included. Categorical variables will be summarized by presenting the number and percentage of participants within each category. Calculation of percentages will exclude missing data as a category. Where appropriate, descriptive statistics may be presented with 95% confidence intervals (CIs).

All tabulations will be based on pooled data across centers.

The data analyses will be performed using SAS for Windows, version 9.4 or higher (SAS, Cary, NC), except where other software may be deemed more appropriate.

CTI Clinical Trial and Consulting Services (Covington, KY) will perform the efficacy and safety analyses described below. Apnimed, Inc., will perform the exploratory analysis pertaining to the OSA endotype endpoints mentioned in Section 2.2.3. Any changes to the analyses that are not

included in this SAP will be documented in the clinical study report (CSR).

4.1. Data Quality Assurance

Once all the source verification is complete, all queries are resolved, and the database has been updated appropriately, the database will be locked and made available to CTI Biostatistics for final analysis.

Data may be made available to CTI Biostatistics for programming purposes prior to database lock at a time when source verification and query resolution is ongoing.

All SAS programs used to create analysis data sets, tables, and listings will be independently programmed by two individuals. The independent SAS outputs produced will be compared, and the SAS programs will be updated until the outputs match.

4.2. Analysis Sets

4.2.1. Enrolled Set

The Enrolled Set is defined as all participants who signed the informed consent form (ICF) (including screening failures).

4.2.2. Modified Intent-To-Treat Analysis (mITT) Set

The mITT Set comprises all participants who are randomized, take at least 1 dose of any of the study treatments, and have at least 1 measurement on the primary endpoint.

Participants will be analyzed for efficacy according to the randomly assigned treatment for each period.

4.2.3. Safety Set

The Safety Set consists of all participants who are randomized and receive at least 1 dose of any of the study treatments. Participants will be analyzed for safety based on the treatment received for each period. Treatment received is defined as the actual treatment taken during each period.

4.2.4. Per Protocol (PP) Set

The PP Set consists of all participants without any major protocol violations that could influence efficacy assessment. Participants in this set will be analyzed according to the treatment they received for each period.

4.3. Assessment Windows

Data will be summarized by the CRF (Study Visit) in which it was collected provided the data is within the windows specified.

4.4. Handling of Dropouts or Missing Data

Missing data will remain missing. No imputation of missing data will be performed.

4.4.1. PSG Parameters

The criteria for use of PSG data will be as follows:

- When TST is < 120 minutes, only TST, time in bed, Stage N1%, Stage N2%, Stage N3%, and Stage R% will be reported. All other PSG indices will be excluded.
- Any AHI and HB parameters during REM will be reported only when the time spent in REM is > 5 minutes.
- Any AHI and ODI parameters in supine position will be reported only when the time spent supine is > 5 minutes.

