7.1.1 Polysomnography

- Methods: Standard overnight PSG recording and data interpretation will be performed in accordance with the American Academy of Sleep Medicine (AASM) scoring manual.
 Participants will be instrumented with standard PSG electrodes. Time of lights out will be established according to the participants' habitual schedule and kept constant across the PSG study nights. The participants will be given 8 hours of time-in bed.
- Scoring: All PSG studies (including screening PSG) will be scored by centralized PSG technologists, blinded to treatment assignment. Scoring will be conducted according to the American Academy of Sleep Medicine manual scoring criteria.

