6.3.2. Sleep Quality VAS

A repeated measures model (see Section 4.7) will be used to model Sleep Quality VAS total score. Model based LS mean estimates will be provided for the following:

- mean score by study treatment (75/2.5 dose, 37.5/2.5 dose, placebo),

- difference in mean score between study treatments (75/2.5 dose vs placebo, 37.5/2.5 dose vs placebo, and 75/2.5 dose vs 37.5/2.5 dose) with 95% confidence intervals and respective p-values (for null hypothesis).

Summary statistics of Sleep Quality VAS total score by study treatment and a by-participant listing will also be provided.

6.3.3. PSG sleep and arousal parameters and alternate measures of AHI, ODI, and HB

Descriptive statistics for the reported value and change from baseline by study treatment will be reported for sleep stages distribution and percentage of time in the various sleep stages (SE, WASO, NAW, SOL, Stage N1%, Stage N2%, Stage N3%, Stage R%). A 95% confidence interval will be included for the change from baseline.

Snoring index, arousal indices (respiratory and spontaneous), fraction of hypopneas (see below) and alternate measures of AHI, ODI, and HB (AHI[4%]: in NREM sleep, in REM sleep, AHI adjusted for position [see below]; AHI[3% or arousal]; HB[3% or arousal]; HB[Total]; ODI[3%]) and will have results provided similar to Section 6.1 (including the model of change from baseline and the descriptive statistics).

Additional clarifying details for the analysis of some of these endpoints is as follows:

- Fraction of hypopneas will be calculated by using the number of hypopneas divided by the total number of apneas plus hypopneas.
- AHI adjusted for position: An additional covariate of % time supine (%TS) will be added to the repeated measures model for AHI(4%).

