7.6. PSG Parameters

PSG safety data will be summarized by presenting descriptive statistics of actual values and changes from baseline by study treatment. PSG safety parameters include total sleep time, heart rate, and total time with $\text{SaO}_2 < 90\%$. A by-participant listing of PSG parameters (including baseline and efficacy parameters) will also be provided.

² In the case that the total correct is 0, the participant will be dropped from the model.

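### The 120-minute sleep cut-off in SAP 4.4.1 removes sleep efficiency, WASO, sleep latency, awakenings and PSG heart rate on very short nights, although none of them needs a minimum sleep time

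*SAP*

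**What the plan says.** SAP 4.4.1 sets the rule for nights with little sleep: "When TST is < 120 minutes, only TST, time in bed, Stage N1%, Stage N2%, Stage N3%, and Stage R% will be reported". The next sentence closes the list: "All other PSG indices will be excluded". Read alone, the word *indices* in that second sentence might mean respiratory event indices only. The word *only* in the first sentence rules that out, because anything not on the kept list is not reported.

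Several planned outcomes are not on the kept list:

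- SAP 2.2.3 names "Sleep Efficiency (SE") and "Wake After Sleep Onset (WASO") as tertiary endpoints, with NAW and SOL beside them.
- SAP 6.3.3 summarises these descriptively by treatment, under "sleep stages distribution and percentage of time in the various sleep stages (SE, WASO, NAW, SOL" and the stage percentages, with a confidence interval for change from baseline. It plans no treatment-comparison model for them.
- SAP 7.6 states that "PSG safety parameters include total sleep time, heart rate" and total time with SaO2 below 90%. TST survives the 120-minute rule; the other two do not.
- Time with SaO2 below 90% is also a modelled secondary endpoint (SAP 6.2.4).

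None of 6.2.4, 6.3.3 or 7.6 makes an exception for short nights. SAP 4.4 adds: "Missing data will remain missing. No imputation of missing data will be performed". Protocol 7.1.1 fixes the recording length: "The participants will be given 8 hours of time-in bed".

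**The concern.** A minimum sleep time protects measures that divide by sleep time. An AHI, ODI, hypoxic burden, arousal index or snoring index from very little sleep is unstable. SE, WASO, SOL, NAW and mean heart rate do not divide by sleep time and can be measured on a short night.

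For SE and WASO the exclusion also depends on the outcome. A night is dropped because the participant slept little, and that is what these measures describe. The cut is made after dosing, on something treatment could change, so the data are not missing at random.

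The kept list is also hard to explain. It retains TST and time in bed but drops their ratio, SE. It retains the stage percentages, whose denominator is the short sleep time itself.

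At stake are the sleep-continuity tables by treatment and the overnight heart-rate summary. With 30 participants, one extreme night can visibly move a treatment mean.

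**Working it through.** The documents give no count or expected frequency of nights under 120 minutes, so there is no planned figure to reproduce. The first step below follows from the documents; the others are illustrations on stated assumptions.

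**1. Which nights the rule removes.** Inputs: cut-off of 120 min (SAP 4.4.1) and time in bed of 8 × 60 = 480 min (Protocol 7.1.1).

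- SE = TST / time in bed. At the cut-off, 120/480 = 25%, so every excluded night has SE below 25%.
- Total wake = time in bed − TST. At the cut-off, 480 − 120 = 360 min, so every excluded night has more than 360 min awake.

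With 480 minutes in bed, the minimum SE shown in the table therefore cannot fall below 25%, whatever happened on the night. SE and total wake on an excluded night can be worked out by hand from the two kept values. SOL, the split of wake between SOL and WASO, NAW and heart rate cannot.

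**2. Effect of one or two excluded nights.** Assumptions: 27 nights per treatment (midway between 30 and 30 × 0.8 = 24, the edge of the planned discontinuation allowance), excluded nights with TST of 90 min, other nights averaging SE 85% and WASO 45 min.

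SE on the short night = 90/480 = 18.75%.

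- One night: (26 × 85 + 18.75)/27 = 82.5%, against 85.0% reported.
- Two nights: (25 × 85 + 2 × 18.75)/27 = 80.1%, against 85.0% reported.

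WASO on the short night depends on how much of the 480 − 90 = 390 min awake came before sleep onset:

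| Assumed SOL | WASO that night | Mean WASO, one night | Mean WASO, two nights |
|---|---|---|---|
| 20 min | 390 − 20 = 370 min | (26 × 45 + 370)/27 = 57.0 min | (25 × 45 + 740)/27 = 69.1 min |
| 200 min | 390 − 200 = 190 min | (26 × 45 + 190)/27 = 50.4 min | (25 × 45 + 380)/27 = 55.7 min |

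The rule would report 45 min in every case.

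**3. Sensitivity to the assumptions.** With n nights per treatment, k of them excluded, the rule raises mean SE by (k/n) × (typical TST − short TST)/480. Take n from 24 to 30, short nights of 60 to 100 min and typical nights of 360 to 400 min.

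- k = 1: from (1/30) × 260/480 = 1.8 points to (1/24) × 340/480 = 3.0 points.
- k = 4: from (4/30) × 260/480 = 7.2 points to (4/24) × 340/480 = 11.8 points.
- k = 0: no effect.

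Mean TST is unaffected throughout, because TST is kept.

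**The case against.** The strongest defence is that the most direct measure of a short night survives. TST is kept, and SAP 7.6 summarises it by treatment with change from baseline as a PSG safety parameter. Protocol 7.2 gives sleep time and sleep stages as its examples of monitored sleep parameters, and TST and stage percentages are what the rule retains. A 90-minute night would lower the mean and minimum TST in the safety table, and SE could be recovered from the kept values. This stands: short nights are not erased. It does not rescue SOL, NAW, the SOL/WASO split or heart rate, and the printed SE and WASO tables would still be truncated.

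A reader might go further and infer that the plan deletes drug-induced insomnia and so flatters the active doses. The documents do not support that:

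- Protocol 7.2 names somnolence as a possible effect of both drugs. Insomnia appears only as an exclusion criterion (Protocol 5.2).
- The rule applies equally to all three treatments, so the direction of any bias is not shown.
- Excluding people with clinically significant insomnia or under 5 hours of typical sleep makes such nights less likely.

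Two further points are fair. The sleep-continuity measures are tertiary and descriptive, and no step of the testing sequence in SAP 4.5 involves them. Excluding time with SaO2 below 90% from the efficacy model is defensible: it is a total with no stated adjustment for sleep time, so a very short night could look falsely good.

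Finally, SAP 4 already calls for n beside each continuous summary, so comparing n for TST with n for hypoxic burden would hint at the loss. That falls short of a stated count of nights under the cut-off.

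**Conclusion.** The rule is broader than its purpose. Read as written, it withholds SE, WASO, SOL, NAW and PSG heart rate on nights under 120 minutes of sleep, and for SE and WASO it selects on the outcome. That every removed night has SE below 25% and over 360 minutes awake rests only on the 480 minutes in bed.

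The effect on reported means depends on assumptions. One such night in 24 to 30 would shift mean SE by roughly 2 to 3 points. In the 27-night example it would hide a rise in mean WASO of about 5 to 12 minutes. The number of such nights is unknown and may be zero, in which case nothing changes.

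The consequence is limited to descriptive sleep-continuity and heart-rate summaries. The point does not challenge the minimum sleep time for hypoxic burden, AHI or ODI, and it does not show that any arm is favoured.

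**What to change.** Reword SAP 4.4.1 as follows:

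- Limit the TST < 120 min exclusion to respiratory, oximetry and other indices with sleep time as denominator: AHI, ODI, hypoxic burden, arousal and snoring indices, and time with SaO2 below 90% in the efficacy model.
- Report SE, WASO, SOL, NAW and PSG heart rate for every recorded night.
- Show time with SaO2 below 90% on short nights only in the safety listing, beside TST, so that it is read against the sleep obtained.
- Give the number of nights under 120 minutes by treatment beside the primary result, since hypoxic burden is lost on the same nights.

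The cost is SAP wording and minor programming; the data are already recorded. The downside is that means become more sensitive to a few extreme nights. The medians already planned in SAP 4 cover that.

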4.4.2. DSST Scores

A DSST total correct of 0 will be dropped from the repeated measures model.

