7.2 Safety Assessments

- Planned time points for all safety assessments are provided in the SoA.
- Safety monitoring will be guided by the established safety profiles of atomoxetine and
 oxybutynin, and by Phase 1 and 2 safety data for the combination. Safety assessments will
 include physical examinations, measurement of vital signs, monitoring and recording of AEs,
 SAEs, and pregnancies, recording of study or treatment discontinuations. Effects on OSA and
 sleep parameters (e.g., sleep time and sleep stages) will also be monitored by PSG.
- Adverse events of special interest include effects on urine outflow, as both atomoxetine and oxybutynin are associated with urinary retention. Effects of atomoxetine on heart rate and blood pressure are expected to be modest, as indicated by the initial data described above, and will also be monitored. Participants with serious cardiac abnormalities will be excluded from the study. Suicidal ideation in children and adolescents is a boxed warning for atomoxetine; however, analysis in adult patients, the target population for the proposed OSA study, did not reveal an increased risk of suicidal ideation or behavior in association with atomoxetine. Daytime sleepiness is both a potential safety outcome and efficacy outcome in OSA. Both atomoxetine and oxybutynin may be associated with somnolence, and oxybutynin is additionally associated with anticholinergic CNS effects such as memory difficulty.

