7. SAFETY ANALYSIS

Safety assessments will include measurement of adverse events (AEs) and serious AEs (SAEs).

The analyses will be descriptive and will be based on the Safety Set. The safety assessments will be summarized by the study treatment the participant actually received within each period.

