7.5. DSST

A repeated measures model (see Section 4.7) will be used to model the natural log of total number of the correct symbol assignments² ($\log(\text{total completed} - \text{total incorrect})$) from the DSST.

Exponentiation of the model-based LS mean estimates of log values will be used to provide the following:

- Geometric mean of DSST by study treatment (75/2.5 dose, 37.5/2.5 dose, placebo), and
- Ratio of (geometric) mean of DSST between study treatments (75/2.5 dose vs placebo, 37.5/2.5 dose vs placebo, and 75/2.5 dose vs 37.5/2.5 dose) with the 95% confidence intervals.

Descriptive statistics of DSST and a by-participant listing (with both raw values and natural log of total complete) will also be provided.

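### The SAP gives two conflicting rules for a DSST score of zero, and under either the zero leaves the DSST model with no sensitivity analysis that keeps it

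*SAP*

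**What the plan says.** SAP 2.2.4 lists the DSST as a safety endpoint. By the schedule of activities it is done only on the mornings after the three crossover nights, so there is no baseline score.

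In SAP 7.5 a repeated measures model "will be used to model the natural log of total number of the correct symbol assignments", defined as items completed minus items incorrect. The results are reported as geometric means by treatment and as between-treatment ratios with 95% intervals.

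Two places say what happens to a zero:

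- SAP 4.4.2, in the section on missing data: "A DSST total correct of 0 will be dropped from the repeated measures model".
- Footnote 2, attached to SAP 7.5 and printed below 7.6: "In the case that the total correct is 0, the participant will be dropped from the model".

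SAP 4.4 adds: "No imputation of missing data will be performed". Outside the model, SAP 7.5 states: "Descriptive statistics of DSST and a by-participant listing (with both raw values and natural log of total complete) will also be provided". No exclusion of zeros is stated for those outputs.

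**The concern.** The score is the trial's only objective test of next-morning performance; the KSS and the sleep quality VAS are self-ratings. The protocol expects a possible effect in this area: "Both atomoxetine and oxybutynin may be associated with somnolence" (Protocol 7.2). A score of zero is the lowest the scoring formula normally allows, and it can arise when every item attempted is wrong. The plan treats that observed result as if it were missing, because of its value and not because of any documented fault in the test. A test not done is already covered by the general missing-data rule.

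The two instructions also remove different amounts of data. SAP 4.4.2 removes one score. The footnote removes a treated person from an analysis based on the Safety Set, so a zero on one dose also takes out that person's valid placebo night and valid night on the other dose. SAP 4.1 requires two independent programmers to work until their outputs match. Each could follow a valid sentence of the SAP and get a different dataset, and the SAP does not say which should give way.

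At stake is whether the reported DSST ratio and its interval describe all observed scores or only those above zero.

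**Working it through.** The documents give no DSST mean, SD, margin or expected number of zeros, so there is no planned figure to reproduce. What can be checked is how each rule acts on data containing a zero.

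**Inputs.** From the documents: 30 participants, three treatments, and discontinuation below 20% (SAP 9), so about 30 × 0.80 = 24 completers. Assumed: a typical score of 50, one zero on one active dose, and no other difference between treatments.

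**Data kept in the model.** 24 × 3 = 72 scores. The rule in SAP 4.4.2 leaves 71. Footnote 2 leaves 72 − 3 = 69, so two valid scores are lost with the zero.

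**Active-to-placebo ratio for that dose.**

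| Handling of the zero | Calculation | Ratio |
|---|---|---|
| Either SAP rule, log model | remaining scores equal | about 1.00 |
| Kept, raw means | 23/24 | 0.958 (4.2% lower) |
| Kept, log(x+1) | exp(−ln 51 / 24) | 0.849 |
| Kept, log(x+0.5) | exp(−ln(50.5/0.5) / 24) | 0.825 |
| Kept, log(x+10) | exp(−ln(60/10) / 24) | 0.928 |

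The log(x+1) figure runs from exp(−ln 61 / 24) = 0.843 to exp(−ln 41 / 30) = 0.884 for typical scores of 40 to 60 and 24 to 30 participants. The last three rows of the table show that the offset matters more than either of those inputs.

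**Direction.** If the zero falls on placebo instead, the model ratio again stays at about 1.00, while the raw-mean ratio with the zero kept is 24/23 = 1.043. Dropping that zero works against the drug.

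**More than one zero.** A small simulation (40 replicates, 30 participants, typical score 50, between-person log-SD 0.2, within-person log-SD 0.1, no drug effect apart from the zeros) gave these 75/2.5-to-placebo ratios. The score-level fit used a random intercept and no visit term, which is simpler than the SAP model. The participant-level figure is a paired geometric mean ratio.

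| Zeros on 75/2.5 | Score dropped | Participant dropped | Kept, log(x+1) | Kept, raw means |
|---|---|---|---|---|
| 0 | 1.01 | 1.01 | 1.01 | 1.01 |
| 1 | 1.01 | 1.01 | 0.89 | 0.98 |
| 2 | 1.00 | 1.00 | 0.77 | 0.93 |
| 3 | 1.00 | 1.00 | 0.68 | 0.90 |

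The two SAP rules gave the same estimate of this ratio. Here the conflict costs valid data and certainty about the dataset; it does not visibly shift the point estimate.

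**Precision when a zero is kept.** With one zero among n pairs and every other difference nil, the mean difference is −D/n and its standard error is also D/n, so t = −1 whatever D is. On log(x+1), D/n = ln 51 / 24 = 0.164, and the 95% interval for the ratio is about 0.60 to 1.19. On the raw scale, D/n = 50/24 = 2.08 points, and the interval is −2.08 ± 2.069 × 2.08, or about −6.4 to +2.2 points. Without the zero, the simulation's within-person log-SD gives a standard error of 0.1 × √2 / √23 = 0.03. A single zero can therefore dominate the interval.

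**The case against.** A reader might infer that severe next-day impairment cannot count against the drug at all. The documents do not support that. The exclusion applies to the model only. Zeros would remain in the raw listing and, with no exclusion stated, in the descriptive statistics, as a minimum of 0 and a lower mean. Evident impairment could also be reported as an adverse event assigned to the most recent treatment (SAP 7.2.1), and self-rated sleepiness is compared by treatment (SAP 6.3.1).

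A reader might also infer that the rule can only move the comparison towards no harm. It cannot be put that way, because the rule applies to placebo nights too. Nor do the documents say whether a zero would reflect impairment, a test not attempted or a test wrongly performed, or how often one is expected.

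The stakes are limited. SAP 7 says of safety: "The analyses will be descriptive and will be based on the Safety Set". DSST is outside the testing sequence in SAP 4.5, SAP 7.5 plans no p-values for it, and no decision depends on the ratio. The footnote may be no more than loose wording for the rule in 4.4.2.

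It is also fair to resist replacing the log model with log(x+1). The primary endpoint uses that offset, but a zero hypoxic burden is the best outcome and lies close to the rest of the scale. A zero DSST would be an extreme outlier, and the result would depend on the offset chosen.

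All of this stands, and it limits the point. It does not remove the conflict between the two rules or supply a model-based analysis that keeps an observed zero.

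**Conclusion.** The point holds in a limited form. SAP 4.4.2 and footnote 2 specify different units of deletion and must be reconciled. Under both, an observed score is excluded because of its value from the only model-based treatment comparison of a named safety endpoint, and no sensitivity analysis retains it.

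The size cannot be fixed from the documents. It is nil if no zeros occur. With one zero among 24 on a dose and typical scores of 50, both assumed, the model would report about 1.00 against a raw mean about 4% lower. The corresponding log(x+1) figure of about 0.85 should not be read as the size of the bias, because it moves between 0.825 and 0.928 as the offset goes from 0.5 to 10. The bias favours the drug only if zeros are commoner on active treatment than on placebo. The documents do not establish that, so the plan cannot be said to be tilted towards the drug.

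**What to change.** Change the SAP wording before unblinding:

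1. Delete the participant-level rule in footnote 2 and state one rule in 4.4.2 and 7.5, so that at most the single score leaves the log model and the person's other nights stay.
2. Set a score to missing only for a documented technical failure or a test not done.
3. Report the number of zeros by treatment beside the model results.
4. Add an analysis that keeps zeros beside the log model, either on the raw number correct or rank-based. SAP 6.1 already does the equivalent for the primary endpoint by repeating the analysis without the transformation.

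The cost is a little more analysis work. An extreme score can widen the interval of a raw-scale analysis, as shown above; ranks limit that influence but do not give a ratio of means. Keeping the log model alongside preserves its precision for the scores above zero.
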